Cognitive Recovery With Cannabis Abstinence Among
High School-Aged Adolescents

NCT03276221

Document Date: 04/28/2023

Cognitive Recovery with Cannabis Abstinence Among High-school-aged Adolescents

Statistical Analysis Plan

The ARCHES Team

NCT: 03276221

First created 2/12/2022

Last revised 04/28/2023

Unblinded analysis 02/03/2023

Version 2.2

Table of Contents

Study Design	4
Participants	4
Order of data collection and creation of the analysis plan	5
Analyst-blind	5
Primary Outcomes.....	7
CANTAB tasks	7
Selection of outcomes.....	10
Statistical model.....	15
Key confirmatory effect.....	16
Multiple comparisons.....	16
Covariates	16
Missing data	17
Clinical Significance	17
Secondary analyses	18
Secondary Outcomes	20
CANTAB tasks	20
Selection of outcomes.....	20
Statistical model.....	21
Power	22
Software	24
References	25

Study Design

The study consisted of a one-month (with a two-month follow-up) longitudinal trial of cannabis abstinence (with data collection from 9/2017 to 12/2022) designed to determine:

1. Whether cognitive performance improves for students abstinent from cannabis use for one month above and beyond any improvement observed for students engaging in continued use.
2. When cognitive performance improves (if improvement during abstinence does occur).
3. Whether cognitive performance in abstinent individuals "returns" to performance levels observed in non-using peers.

Participants

The study planned to recruit 210 adolescents across the following conditions:

1. A control group of non-cannabis users (Non-users; n = 70).
2. Regular users of cannabis (n = 140) randomized to either...
 - a. Contingency management intervention that incentivized 4 weeks of cannabis abstinence (CB-Abst; n = 70).
 - b. Non-contingent monitoring with no abstinence requirement (CB-Mon; n = 70).

All participants completed cognitive assessments, toxicology testing, self-report questionnaires and semi-structured mood and substance use interviews during the 4-week study as well as one 30-day follow-up visit. Abstinence was verified using the statistical model of Schwilke and colleagues (2011). The approach differentiates residual cannabinoid excretion from new cannabis exposure by comparing observed urine metabolite ratios against expected ratios. Observed ratios that exceed a 95% confidence interval indicate new cannabis use.

Order of data collection and creation of the analysis plan

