We acknowledge that under ideal circumstances outcomes should be clearly defined along with a corresponding analysis plan prior to any data collection. We note that for this study, specific primary outcomes were defined and the analytic plan written near the end of the 5-year data collection, and for full disclosure, that 4 papers had already been published on data collected from the study.

- [name] and colleagues (2020) created a pharmacokinetic model of THC elimination using data on urine metabolites.
- [name] and colleagues (2021) examined alcohol use over the month of abstinence and the follow-up session.
- Cooke and colleagues (2021) examined anxiety and depression symptoms over the month of abstinence and the follow-up session.
- Savulich and colleagues (2021) examined sex differences over a variety of baseline characteristics, including cognitive outcomes.

Despite this order of events, the outcomes and analysis plan proposed here remain confirmatory in nature, because, in the one case that cognitive outcomes were examined, they were only examined at baseline.

Analyst-blind

To better ensure confirmatory conclusions, and to avoid unconscious bias towards adjustments that favor statistical significance, initial implementation of analyses was 'analyst-blind' (Dutilh, Sarafoglou, & Wagenmakers, 2019). In other words, analyses were first implemented on data where intervention status (whether a participant was in the CB-Abst or CB-Mon group) had been randomly shuffled. Data was shuffled by an individual outside the core ARCHES team. Only after data exclusion criteria had been determined, transformations of

predictor and outcome variables had been finalized, models had been properly specified, and any other unforeseen circumstances addressed, was the un-shuffled data provided to the analyst for the final analysis implementation.

Notable changes made during the analyst-blind period were:

- Removal of number of years spent using cannabis as a covariate. This measure was dropped due to its high correlation with a participant's overall age.
- The decision to only examine a linear trend for change over time. This decision was made due to the small number of time points (a quadratic time trend requires 3 parameters, but there were only 4 time points to estimate this trend).

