Continuous outcomes (e.g., latencies and reaction times) were fit using a standard linear regression model. Bounded count outcomes (e.g., number of errors or correct responses) were fit using binomial regression. Specifically, let $y_{(p,t)}$ refer to the outcome value for participant p at time t , where $y_{(p,t)} = \{0, 1, \dots, H\}$ with H referring to the highest possible value. We assumed that $y_{(p,t)}$ was distributed according to a binomial process governed by a latent probability $\theta_{(p,t)}$:

$$y_{(p,t)} \sim \text{Binomial}(\theta_{(p,t)}).$$

The log-odds of this latent probability can then be decomposed into the weighted sum of the predictors of interest.

In contrast to linear regression, which includes a parameter for the residual standard deviation, binomial regression has no additional parameter to handle overdispersion. While failure to account for overdispersion can lead to underestimation of standard errors, as noted before the GEE approach is robust to misspecification of distributional assumptions and corrects for this underestimation, and as such we did not need to implement any additional steps to address overdispersion issues.

Key confirmatory effect

The key confirmatory effect of interest for each outcome will be a dummy-coded contrast between CB-Mon (the referent, coded as 0) and CB-Abst (coded as 1), testing whether a constant effect of abstinence exists, averaged over all time points.

Multiple comparisons

Each module/task from the CANTAB examines a separate cognitive process of interest. We therefore address multiple comparisons issues within each module. As the number of outcomes per module range from 1 to 4, we used a simple Bonferroni correction, dividing the desired error rate of 5% by the number of outcomes per module. Therefore, effects of interest were flagged as statistically significant for $\alpha = 0.05$ (for the SST module), $\alpha = 0.025$ (for the PAL, SSP, OTS, and SWM modules), $\alpha = 0.0167$ (for the VRM module), and $\alpha = 0.0125$ (for the MTT module).

Covariates

The covariates we included for the primary analysis were:

- A coefficient for a linear trend to capture change over time, coded as week 1 = -3, week 2 = -1, week 3 = 1, and week 4 = 3.
- A subject's baseline value for a given outcome, converted to a z-score.

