In other words, we assume a conservative additive model, adjusting for baseline levels and with main effects for a) the impact of abstinence and b) change over time, but no treatment by time interaction.

Additionally, to assess the robustness of our conclusions we will incorporate, at a minimum, the following covariates as part of a secondary analysis:

- Age of participant at baseline (in years).
- Biological sex (male versus female).

Baseline scores from the Cannabis Use Disorder Identification Test - Revised (CUDIT-R; Adamson et al., 2010). The CUDIT-R is an 8-item scale with scores ranging from 0 to 32, where higher scores indicate more problematic cannabis use (a score of 8 or higher indicates hazardous use, while a score at or above 12 indicates a possible use disorder).

Missing data

Missing outcome data (e.g., subjects who did not complete all four visits or did not complete all 7 modules during a visit) will be handled using multiple imputation via chained equations (MICE; see for example Azur, Stuart, Frangakis, & Leaf, 2011). Missing outcome values will be imputed 48 times using linear regression and predictive mean matching. We will then apply the statistical model to each combination of observed and imputed data and will pool the resulting set of 48 model results using Rubin's rule. Subjects must have at least one post-baseline data point to be included in an analysis. Note because we are interested in the effect of abstinence, only data with biochemically-verified abstinence will be included – all data for the visit of and subsequent visits in which abstinence was no longer verified will be excluded for CB-Abst subjects. Covariates for imputing missing values will be:

- Non-missing outcome values at other time points;
- Outcome values at the baseline visit;
- The covariates listed above (age in years, biological sex at birth, baseline scores for CUDIT-R, and duration in years spent using cannabis).

Clinical Significance

In addition to determining whether there is a statistically significant difference between groups, we assessed clinical significance by computing standardized effect sizes for all contrasts of interest per each outcome. Effect sizes were estimated by dividing the estimate (transformed when necessary to be in the original scale of the measure) by the standard

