deviation of the outcome pooling over groups during the baseline visit. In other words, we normalized the contrast of interest by the baseline variation in the outcome.

Secondary analyses

We conducted the following secondary analyses:

1. We tested our assumption of an additive model by fitting a model that includes a group by time interaction (i.e., the product of the contrast between CB-Abst and CB-Mon and the linear time trend variable). We conducted an omnibus test comparing the simpler additive model to the more complex interaction model – if the associated Wald test is significant at $p < \alpha_M$ (i.e., the specified level of significance α for a given module M) this will indicate the presence of a group by time interaction. Post-hoc comparisons of the regression coefficients of the interaction model will also indicate, if abstinence was associated with improvements in cognitive performance, when such improvement occurred. This secondary analysis addresses the second research question of the study.
2. We examined how cognitive performance of the two groups of cannabis users (the contingency management and monitoring groups) also compares against the control sample of non-users. This secondary analysis addresses the third research question of the study. We therefore...
 - a. Analyzed data from all three groups.
 - b. Created two dummy-coded variables to represent the 3 levels (contingency management, monitoring, and non-users) for group status. We used the non-user group as the referent, and had separate variables for the CB-Abst and CB-Mon groups.
 - c. Assessed (1) an additive model (main effects for group and time), and (2) an interaction model (also including at the group x time interaction in addition to the main effects).

- d. Conducted an omnibus test comparing the simpler additive model to the more complex interaction model – if the associated Wald test is significant at $p < \alpha_M$ (i.e., the specified level of significance α for a given module M), this will indicate the presence of a group by time interaction.
- e. If a group by time interaction or a main effect of group was found, we ran post-hoc comparisons to examine (a) if the CB-Mon group had worse performance compared to the non-user group, (b) if the CB-Abst group did not differ compared to the non-user group or (c) if performance for the CB-Abst group improved to levels matching the non-user group.

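### The SAP says its linear group-by-time model will show when cognition improves, but that model cannot locate the week of a non-linear change

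*SAP*

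**What the plan says.** The SAP's Study Design section lists three questions; the second is the timing of any improvement during abstinence. Under Analyst-blind, the notable changes include "The decision to only examine a linear trend for change over time", for the reason that "a quadratic time trend requires 3 parameters, but there were only 4 time points to estimate this trend".

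Under Covariates, time is a single linear term, "coded as week 1 = -3, week 2 = -1, week 3 = 1, and week 4 = 3". Baseline is not a time point; it enters as "A subject's baseline value for a given outcome, converted to a z-score". The primary model has main effects of group and time "but no treatment by time interaction".

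Secondary analyses, item 1, adds one interaction term, "the product of the contrast between CB-Abst and CB-Mon and the linear time trend variable". The SAP then states that "Post-hoc comparisons of the regression coefficients of the interaction model will also indicate" when improvement occurred, if abstinence proves to be associated with improvement, and that this addresses the second question. Item 2 fits a group-by-time interaction in all three groups and names no other form for time. No analysis in the SAP treats week as a factor.

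**The concern.** A timing question needs a model in which the group difference can take different shapes over the weeks. With one linear product term, every week-specific difference read off the model is forced onto a straight line. If the true course is a jump followed by a plateau, or a late jump, the fitted weekly differences will be misdated, and nothing in the planned output would show it. A stated question of the trial could then be reported with recovery placed in the wrong week.

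The reason given for staying linear does not rule out a more flexible model. Three parameters are fewer than four time points, and four visits identify four means per group.

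**Working it through.** **1. Inputs.** Time codes c = -3, -1, 1, 3 (SAP, Covariates). Working independence between a subject's visits (SAP, Statistical model). 70 per group and 4% weekly drop-out (SAP, Power). Test-retest correlation r = 0.6 to 0.75 (protocol, Biostatistical Analyses).

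**2. The plan's own figure.** The SAP gives 80% power at two-sided 0.05 for a slope difference of 11 ms/week in mean latency on the Attention Switching Task. The variance components are not printed, so this cannot be reproduced. The parts that can be checked:
- 0.96^4 = 0.849, matching just under 85% retention.
- 11/21 = 52% and 67/160 = 42%, as stated.
- 12/25 = 48% against a stated 50%, which rounded inputs could explain.

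Inverting the figure gives SE = 11/(1.960 + 0.842) = 3.93 ms/week and noncentrality 2.802² = 7.85.

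**3. What the interaction model can represent.** Let y be the CB-Abst minus CB-Mon difference at weeks 1-4. On the identity scale with balanced data, the model fits mean(y) + b·c, with b = Σ(c·y)/20, since 9 + 1 + 1 + 9 = 20.

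| True weekly difference | Mean | b | Fitted weeks 1-4 |
|---|---|---|---|
| 0.25, 0.50, 0.75, 1.00 | 0.625 | 2.5/20 = 0.125 | 0.25, 0.50, 0.75, 1.00 |
| 0, 0.75, 1.00, 0.75 | 0.625 | 2.5/20 = 0.125 | 0.25, 0.50, 0.75, 1.00 |
| 0.50, 0.25, 0.50, 1.25 | 0.625 | 2.5/20 = 0.125 | 0.25, 0.50, 0.75, 1.00 |
| 0, d, d, d | 0.75d | 3d/20 = 0.15d | 0.30d, 0.60d, 0.90d, 1.20d |
| 0, 0, 0, d | 0.25d | 3d/20 = 0.15d | -0.20d, 0.10d, 0.40d, 0.70d |
| d, d, d, d | d | 0 | d, d, d, d |

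The first three rows are a steady gain, a week-2 jump with a rough plateau, and a late jump. They give the same fitted line. In the fourth row, 30% of the effect appears at week 1, where there is none, and week 4 is overstated by 20%.

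Of the 17 outcomes, 12 are binomial (all eight memory outcomes; four of nine executive ones). For these the projection applies to log-odds, approximately.

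**4. Is a week factor estimable?** Two groups by four weeks is 8 cell means, and the design has rank 8. The interaction takes 3 df instead of 1.

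**5. Power cost.** Using noncentrality 7.85, a truly linear difference and complete data (noncentral chi-square):

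| Alpha | 1 df | 3 df |
|---|---|---|
| 0.05 | 80% | 65% |
| 0.025 | 71% | 54% |
| 0.0125 | 62% | 44% |

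**6. Precision of weekly estimates.** With n at week w = 70 × 0.96^w, compound symmetry (an assumption) and 80% power:
- Baseline-adjusted difference at one week, (z_α/2 + 0.842)·√(1 - r²)·√(2/n): 0.32-0.41 SD at alpha 0.05; 0.38-0.49 SD at 0.0125.
- Change between adjacent weeks, (z_α/2 + 0.842)·√(2(1 - r))·√(2/n): 0.35-0.46 SD at alpha 0.05; 0.42-0.55 SD at 0.0125.

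**The case against.** The strongest reply is that the interaction model is not silent on timing. It has two group coefficients, a mean difference and a slope, and together they separate an effect present by week 1 and constant from one that grows. That stands. A reader might infer that the second question is unanswerable as planned; the SAP does not support this, because a coarse answer is available.

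Two related inferences also fail. One is that steps at week 2 and at week 4 are confused because both give slope 0.15d. Their means are 0.75d and 0.25d, so the model misfits each but tells them apart. The other is that a zero slope hides early recovery. A zero slope with a non-zero group effect is the correct description of an effect complete by the first test, and it is the effect the primary contrast targets.

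The linear-only decision can also be defended as parsimony, made blind; the SAP does not say that other shapes are unidentifiable. That is fair, and it is a reason to qualify the rationale rather than delete it. Blinding protects against bias in choosing the model, but it does not fit the model to the question.

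Third, protocol Aim 3 contrasts about 4 days with 30 days, and the linear contrast weights the first and last visits most. So Aim 3 is related to the SAP's second question but is not identical to it.

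Finally, a week factor brings its own problems. Testing each of four weeks at the module alpha would raise the within-module Bonferroni bound from 5% to about 20% (SST: 4 × 0.05; PAL: 2 × 4 × 0.025). The model would also be new after unblinding. Both points stand and shape the fix.

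**Conclusion.** The concern holds in a limited form. The statement in Secondary analyses, item 1, promises more than its model can deliver: timing is answered only under an assumed straight line over weeks 1-4. The three-group interaction appears to share the limit, since it names no other form of time. The averaged confirmatory contrast is unaffected.

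The size is shown by three quite different courses with one fitted line, and by a week-2 step that is misstated by 0.30d at week 1 and 0.20d at week 4. These figures assume balanced data on the identity scale.

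A reader might infer that a week factor would settle the question. The documents do not support that either. At the SAP's own detectable slope a 3-df test has roughly 44-65% power across alphas of 0.0125 to 0.05. Neither model can date a gain between baseline and the first post-baseline test, at about day 5. Later weeks also hold a reduced and selected CB-Abst group, because visits from the loss of verified abstinence onward are excluded. The week factor removes the straight-line constraint; it does not guarantee an answer.

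**What to change.** - Keep the additive primary model and the 1-df linear interaction test.
- Add a secondary group-by-week model with week as a four-level factor, in both the two-group and three-group analyses. Label it as added after the 02/03/2023 unblinding; the SAP already discloses one such change (VRM immediate recall).
- Report the CB-Abst minus CB-Mon difference at each week with its confidence interval, as estimates and without a significance flag per week. If weekly tests are wanted, divide the module alpha by a further four.
- In Secondary analyses, item 1, limit the claim to timing under an assumed linear trend.
- Keep the rationale under Analyst-blind as a record, with a note that four visits do support four means per group.
- State beside the weekly results that gains before the first test stay undated and that CB-Abst shrinks selectively.

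The cost is one extra model per outcome in each analysis (four more parameters with two groups, six with three), wider weekly intervals, and lower power if the 3-df interaction is tested. No new data are needed.

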## II. SPECIFIC AIMS

**Aim 1:** To provide updated information on prevalence and frequency of cannabis use in relation to other forms of substance use in a representative sample of school-aged children and adolescents.

**Aim 2:** To evaluate the effect of contingency management on initial 30-day verified cannabis abstinence in children and adolescents and older adolescents who use cannabis at least weekly and are not seeking treatment.

**Aim 3:** To determine whether there is cognitive dysfunction in cannabis use that persists in the short term (4 days) after use but resolves with extended abstinence (30 days) compared to cannabis users who do not quit and non-using controls.

**Aim 4:** To estimate the rate of cognitive improvement with cannabis abstinence as a function of time since last use and concentration of detectable cannabis metabolites in urine.

**Aim 5:** To assess the neural correlates of cannabis abstinence using structural and functional brain imaging measures.

**Aim 6:** To explore the effects of cannabis abstinence on objective and subjective measures of sleep quality.

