##### **Cannabis-Using Group:**

1. Use of cannabis at least once per week on most weeks
2. Cannabis use reported within 7 days of both baseline visits.
3. No immediate plan to discontinue cannabis use.

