At the first and second baseline visits, all cannabis using participants will be using cannabis as usual. At the end of the second baseline, half of the cannabis using participants (n=150) will be randomly assigned to 30 days of monitoring and half of the cannabis users will be randomly assigned to 30 days of contingency management (n=150). Cannabis using participants assigned to the monitoring condition will not be asked to abstain from cannabis use (but may freely do so if they wish) and will be compensated with vouchers for session attendance as will non-users. Cannabis using participants assigned to contingency management will be asked to abstain from cannabis use for one month after the second baseline and will complete a behavioral contract that lists behaviors to be monitored, schedule of monitoring and contingencies to be imposed.

Contingency management participants will be reimbursed using a two-track incentive system: they will receive vouchers of progressively escalating values for both session attendance and cannabis abstinence (indexed by self-reported non-use and progressively decreasing quantitative levels of urine THCCOOH). The schedule of reimbursement for session attendance and abstinence has been reported effective in similar populations. Participants are reset to the starting level when abstinence is not demonstrated. Cannabis using participants in the monitoring condition will receive vouchers of progressively escalating values for session attendance only. Non-using participants (n=100) will be assessed using identical study procedures (with the exception of being asked to change cannabis use) and will be compensated for session attendance similar to those in the cannabis monitoring condition. All compensation will be distributed between study visits. All participants will engage in a brief end-of-study debriefing visit.

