## **VI. BIOSTATISTICAL ANALYSES**

We will use a proportional hazards model to evaluate time to relapse as the dependent variable and potential predictors (e.g., baseline cognitive function, demographics, substance use severity, mental health) as independent variables. We will use time to relapse instead of 30-day abstinence because differentiating between early and late relapsers may increase power.

To determine whether improvements in cognitive function with abstinence will be greater after 30 days than after 4 days among individuals who quit using cannabis compared to those who do not quit and non-users, repeated measures analysis of covariance will be conducted comparing groups on each cognitive measure across the testing sessions controlling for relevant covariates and using an unspecified covariance structure. We will test whether the difference in cognition after 4 and 30 days of abstinence among those who discontinue cannabis use will be greater than the same difference among children and adolescents who do not stop using cannabis and non-users.

For longitudinal analyses aimed at better understanding the time course of cognitive change with cannabis abstinence, we will conduct mixed-effects regression models with cognitive performance as the outcome variable. Models will include both fixed effects and random effects to account for repeated assessment over time. Random effects will include intercepts, allowing for individual differences in baseline cognitive performance, and slope, allowing for individual differences in the rate of change of cognitive function across assessments. Fixed effects will include group, time since last use, amount of detectable cannabis in urine, and relevant static and time-varying covariates. Two-way interactions between time since last use and group as well as amount of detectable cannabis and group will also be included as fixed effects in the model.

**Power Analysis:** Test-retest properties of the primary proposed cognitive instruments repeated 1 to 8 weeks apart ranged from 0.6 to 0.75. We normalized the difference that we can detect by the population standard deviation of each test to calculate the detectable "effect size." Which range from 0.51 to 0.65 with a two-sided

alpha of 0.05 and 80% power. Dropouts will be considered to be non-abstinent for Aim 1. These results will be used to generate effect estimates specific to non-treatment seeking child and adolescent cannabis users.

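### The SAP asks about abstinence versus continued use but tests against the whole monitoring arm, whose members may stop, and never reports how much of that arm was abstinent

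*SAP*

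**What the plan says.** **The question.** SAP, Study Design, question 1 asks whether abstinent students improve "above and beyond any improvement observed for students engaging in continued use". Protocol Section II, Aim 3, sets abstinence against the course "compared to cannabis users who do not quit and non-using controls".

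**The control arm.** SAP, Participants, defines it as "Non-contingent monitoring with no abstinence requirement (CB-Mon; n = 70" per arm. Protocol Section V, Active Study Phase, says that monitoring participants "will not be asked to abstain from cannabis use (but may freely do so if they wish".

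**The test.** SAP, Key confirmatory effect, specifies "a dummy-coded contrast between CB-Mon (the referent, coded as 0) and CB-Abst (coded as 1" and presents the result as a constant effect of abstinence over the four weekly time points.

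**Use of verification.** SAP, Missing data, removes a CB-Abst participant's data from the first visit at which abstinence is no longer verified. It has no counterpart for CB-Mon. None of the four items under Secondary analyses (interaction, non-user comparison, covariates, observed data only) considers use in CB-Mon.

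**The protocol's own analyses.** Protocol Section VI groups people by behaviour. It asks whether the change among those who discontinue is "greater than the same difference among children and adolescents who do not stop using cannabis and non-users". It also plans a mixed model with time since last use and urine cannabis level, each interacted with group.

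**The concern.** The question and the test have different comparators. A monitoring participant who stops is outside the comparator of research question 1, Aim 3 and Protocol Section VI, but inside the referent of the SAP contrast. The SAP treats actual use as decisive in one arm and does not look at it in the other.

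The comparison with the randomised monitoring arm is not itself at fault. What is at stake is the conclusion drawn from it. A null result could be reported as showing that a month of abstinence adds nothing beyond continued use, when the comparator was a mixture of continued use and abstinence in unknown proportion. The same arm-based CB-Mon group also enters the comparison with non-users.

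**Working it through.** **Inputs from the SAP (Power; Multiple comparisons).** 70 per arm; 4% drop-out per week; 80% power at two-sided 0.05 for CB-Abst versus CB-Mon differences of 11, 12 and 67 ms/wk; pilot effects of 21, 25 and 160 ms/wk; test level 0.0125 for the MTT module.

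**Assumed, because the documents give no figure.** q, the share of CB-Mon visits that are abstinent.

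**Step 1: the plan's own figures.** Retention is 0.96^4 = 0.849, as stated. The ratios are 11/21 = 52.4%, 12/25 = 48.0% (stated 50%, within rounding of its inputs) and 67/160 = 41.9%. The 80% itself cannot be rebuilt, because the variance components are not given. Taken as stated, it implies a standard error of 11/(1.960 + 0.842) = 11/2.802 = 3.93 ms/wk. The three differences are stated as CB-Abst versus CB-Mon, so nothing here shows them to be wrong.

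**Step 2: dilution.** If the retained CB-Abst visits are all abstinent and an abstinent CB-Mon visit carries the full effect, the expected contrast is (1 − q) × effect. For an effect that would have 80% power at q = 0:

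power(q) = Φ((1 − q) × 2.802 − z), with z = 1.960 at level 0.05 and 2.498 at level 0.0125.

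| q | Contrast if the true effect is 11 ms/wk | Power at 0.05 | Power at 0.0125 |
|---|---|---|---|
| 0 | 11.0 | 80% | 62% |
| 5% | 10.4 | 76% | 57% |
| 10% | 9.9 | 71% | 51% |
| 20% | 8.8 | 61% | 40% |
| 30% | 7.7 | 50% | 30% |

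Worked line: at q = 10% and level 0.05, 0.90 × 2.802 − 1.960 = 0.561, and Φ(0.561) = 0.713.

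**Step 3: a large effect.** At the pilot's 21 ms/wk, 21/3.93 = 5.35 standard errors. With q = 30%, power is Φ(0.7 × 5.35 − 1.960) = 96%.

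**Step 4: the opposing force.** Let D be the true effect in SD units, f the share of CB-Abst data removed, and s the amount by which retained CB-Abst data would differ from removed data, in SD units, for reasons other than abstinence. All are assumed, and the effect of imputation is ignored. The net bias is −q × D + f × s.

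- D = 0.3, q = 0.20, f = 0.1, s = 0.2: −0.06 + 0.02 = −0.04
- D = 0.3, q = 0.10, f = 0.2, s = 0.2: −0.03 + 0.04 = +0.01
- D = 0.3, q = 0.10, f = 0.3, s = 0.3: −0.03 + 0.09 = +0.06
- D = 0: no dilution, and the bias is f × s, +0.02 to +0.09 for these (f, s) pairs

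The sign changes within ordinary values.

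**The case against.** The strongest reply is that a randomised arm is a sound referent, that CB-Mon is openly described as having no abstinence requirement, and that entry limits spontaneous quitting. Participants must have "No immediate plan to discontinue cannabis use" and must report use within 7 days of both baseline visits. A large effect would also survive heavy dilution (step 3). All of this stands. It limits the size of the problem, but it does not make monitoring the same as continued use, and it does not supply q.

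Three stronger readings are tempting, and the documents do not support them.

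- *A reader might infer that the effect of abstinence is understated.* That needs a true effect, a non-trivial q and no offsetting bias. The removal of unverified visits in CB-Abst alone sets a selected group against an unselected arm and can inflate the contrast. The two mechanisms are also linked: the factor (1 − q) holds only because of that removal. Without it, the factor would be the abstinent share in CB-Abst minus q.
- *A reader might infer that no planned analysis looks at use in CB-Mon.* That is true of the SAP only. The mixed model in Protocol Section VI uses actual exposure in every group.
- *A reader might infer heavy dilution at the first post-baseline test, about 5 days after the second baseline.* Entry asks only for "Use of cannabis at least once per week on most weeks", so a minimum-frequency user may not have used since baseline. But such a user is still continuing use, and Aim 3 expects dysfunction to persist about 4 days after use. That visit cannot be credited with the full effect, and no distribution of use frequency is given.

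**Conclusion.** The mismatch is real and worth correcting. As planned, the contrast is neither the as-randomised effect of contingency management, because CB-Abst visits are removed, nor abstinence versus continued use, because CB-Mon is unclassified.

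Taken alone, dilution would lower power from 80% to 76%, 71% and 61% at q = 5%, 10% and 20%. This rests on an assumed q, on retained CB-Abst visits being fully abstinent, on abstinent CB-Mon visits carrying the full effect, and on a true effect exactly at the 80% point. The net direction of bias cannot be settled from the documents. The risk lies in moderate effects and in how a null result is read.

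**What to change.** In SAP, Secondary analyses, and in the wording of the main conclusion:

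1. Apply the urine metabolite-ratio model used for CB-Abst, together with the timeline follow-back interview, to CB-Mon at each week, and report the share of CB-Mon visits verified abstinent.
2. State the result of the key confirmatory contrast as *versus monitoring*, not *versus continued use*.
3. Add a secondary as-randomised estimate for each primary outcome, using all visits in both arms. It is the between-arm difference in outcome divided by the between-arm difference in verified-abstinent proportion (instrumental variable with arm as instrument, baseline value and week as covariates, standard errors clustered by participant). For the 12 of 17 outcomes modelled as binomial, report a mean difference on the original scale or use a matching nonlinear method. Label the estimate post hoc, because the SAP dates the unblinded analysis 02/03/2023. State that it is the effect in those whom the incentive moved to abstain, and that it assumes contingency management affects cognition only through abstinence.
4. Keep the exposure-based analyses of Protocol Section VI and state how they relate to the SAP contrast. Recasting them by randomised arm would discard the comparison closest to Aim 3. Dropping abstinent CB-Mon participants is not a clean alternative, since it adds post-randomisation selection in the second arm.

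**Cost.** SAP text, one descriptive table and one added analysis. Urine is quantified and use is interviewed in every arm, so no new data are needed. The downsides of item 3 are a wider interval, an exclusion assumption that reduced use short of abstinence would strain, and post hoc status. Items 1 and 2 alone would correct the interpretation at almost no cost.
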